**PARTNERS HUMAN RESEARCH COMMITTEE
DETAILED PROTOCOL**

PRINCIPAL/OVERALL INVESTIGATOR

[name].

PROTOCOL TITLE

A Randomized Controlled Trial of an Advanced Care Planning Video Decision Support Tool for Patients with End-Stage Liver Disease (Clinicaltrials.gov Identifier NCT03557086)

FUNDING

NIH-NIDDK National Institute of Diabetes and Digestive and Kidney Diseases
4K24DK078772-10

VERSION DATE

Version 9: February 6, 2020

A Randomized Controlled Trial of an Advanced Care Planning Video Decision Support Tool for Patients with End-Stage Liver Disease

Version 9: February 6, 2020

SPECIFIC AIMS

The goal of this pilot randomized trial is to assess the feasibility and preliminary efficacy of an advanced care planning (ACP) video decision support tool for improving patients' knowledge regarding their goals of care options and end of life (EOL) decision-making in patients with end-stage liver disease (ESLD).

Aim 1: To assess the feasibility and acceptability of an ACP video decision support tool for patients with ESLD

- *Hypothesis 1: The intervention will be deemed feasible and acceptable if at least 60% of eligible patients are enrolled in the study and if at least 60% of patients randomly assigned to the video intervention report that the video is acceptable*

Aim 2: To assess the impact of an ACP video decision support tool on patients' knowledge about their EOL care options

- *Hypothesis 2: Patients randomly assigned to the video intervention will report improved knowledge of their EOL care options compared to those randomized to the verbal narrative control*

Aim 3: To assess the impact of an ACP video decision support tool on patients' preferences for EOL care

- *Hypothesis 3: Patients randomly assigned to the ACP video will be more likely to prefer comfort care compared to those randomized to the verbal narrative control arm*
- *Hypothesis 4: Patients randomly assigned to the video intervention will be more likely to forgo cardiopulmonary resuscitation (CPR) and intubation compared to those randomized to the verbal narrative control arm*

Aim 4: To assess the impact of an ACP video decision support tool on patients' documented EOL care preferences

- *Hypothesis 5: Patients randomly assigned to the video intervention will be more likely to have their code status documented in the electronic healthcare record compared to those randomized to the verbal narrative control arm*

BACKGROUND AND SIGNIFICANCE

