We will collect and enter all patient data electronically using Research Electronic Data Capture (REDCap). The REDCap Survey is a tool for building and managing online surveys. Vanderbilt University, in collaboration with a consortium of institutional partners, has developed this software and workflow methodology for electronic collection and management of research and clinical trial data. Our research team has extensive experience using REDCap and will create and design the surveys in a web browser, with institutional information technology support. The REDCap Survey system offers secure, HIPAA compliant, web-based applications that provide an intuitive interface for participants to enter data, with real-time validation rules at the time of entry.

Participants will use tablet computers to complete questionnaires in clinic. If any participants refuse or are unable to complete the questionnaires on the computer, they will be permitted to use hard-copy paper versions. In addition, the patient data collected from the electronic health record will be abstracted throughout the study and directly inputted into REDCap.

Study Outcomes

- **Primary Outcome:** The primary outcome is feasibility. The proposed video intervention will be deemed feasible if at least 60% of eligible patients are enrolled in the study. The 60% feasibility cut-off is commonly used in behavioral intervention studies.⁵¹⁻⁵³
- **Secondary Outcomes:** The secondary outcomes will include patients' comfort/satisfaction with the video, patients' stated post-intervention EOL care preferences categorized as four options: Life-prolonging care, limited medical care, comfort care, or unsure; individual preferences for CPR and intubation before and after intervention in the verbal narrative and video groups; and change in knowledge scores after receiving the verbal narrative or video

Sample Size Calculation

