We will randomize up to 70 patients with ESLD for this project. The primary endpoint of the study is feasibility. We chose the sample size of 70 patients based on the feasibility of completing the project during the proposed timeframe and the ability to assess the preliminary efficacy of the intervention. Consistent with the behavioral intervention literature, at least 20 patients are needed in each group in a pilot study to estimate a parameter.^{54,55} Therefore, the proposed sample size will provide us with preliminary data that can be utilized to determine the effect size and adequately power future randomized trials. This is a commonly utilized study design for pilot testing of behavioral interventions and is consistent with the National Institute of Health Stage Model for Intervention Development. While the feasibility of the intervention can be assessed using a single-arm design, preliminary efficacy is better assessed utilizing a control group as we are proposing in this trial.

A Randomized Controlled Trial of an Advanced Care Planning Video Decision Support Tool for Patients with End-Stage Liver Disease

Analysis Plan

We will report baseline demographic and clinical characteristics of all study participants using means and proportions to describe continuous and categorical variables, respectively. Because this is a pilot study, we will use conservative ($\alpha = 0.05$) and liberal ($\alpha = 0.20$) critical values to assess statistical significance between the two arms in this pilot study.

Aim 1: The primary endpoint of the proposed study is feasibility. The proposed video intervention will be deemed feasible if at least 60% (95% CI +/- 13.6%) of eligible patients are enrolled in the study and complete at least 60% of the intervention sessions. The proposed video intervention will be deemed acceptable if at least 75% of patients randomized to the intervention arm report satisfaction and comfort with the video.

Aim 2: Changes in knowledge scores from before and after the intervention will be compared between the two groups using two-sample t-tests.

Aim 3: Post-intervention EOL care preferences (life-prolonging care, limited medical care, and comfort care), CPR preferences, and intubation preferences will be compared between the two groups using Fisher's exact tests. The change in CPR and intubation preferences before and after the intervention within each group will be compared using McNemar tests.

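### Aim 3's between-arm test leaves out the baseline preferences, which costs precision, and the within-arm McNemar tests are not labelled descriptive

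*Combined protocol and SAP*

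**What the plan says.** Hypotheses 3 and 4 (Specific Aims, Aim 3) are statements about the difference between arms. For Hypothesis 4, video patients are expected to be "more likely to forgo cardiopulmonary resuscitation (CPR) and intubation compared to those randomized to the verbal narrative control arm".

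The Analysis Plan gives Aim 3 two analyses:

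- **Between arms:** post-intervention EOL care preferences, "CPR preferences, and intubation preferences will be compared between the two groups using Fisher's exact tests".
- **Within arms:** "The change in CPR and intubation preferences before and after the intervention within each group will be compared using McNemar tests".

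Study Outcomes lists, as a secondary outcome, "individual preferences for CPR and intubation before and after intervention in the verbal narrative and video groups". The Data Collection Timeline (Table 1) shows all three preference items asked at baseline and again after the intervention, and Randomization places the baseline questionnaire before allocation.

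No sentence brings a baseline preference into a comparison of the arms, and baseline EOL preference has no planned analysis beyond description. Aim 2 differs: there, the change in knowledge score is compared between arms.

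**The concern.** Two things follow from this layout.

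First, a patient's wish about CPR before the video is likely to be the best available predictor of the wish minutes later. A between-arm test that ignores it carries all the patient-to-patient variation in starting wishes. Sample Size Calculation says the pilot should give preliminary efficacy data and an effect size for later trials, so precision of the arm difference matters.

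Second, a McNemar test asks whether one arm moved from its own baseline. The control arm hears the same script as the video (The Control Arm; Appendix C), so both arms may well move. A pair of p-values, one significant and one not, says nothing direct about the difference between arms, yet it is easily read as a video effect. The plan does not warn against that reading.

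**Working it through.** The documents give no power, effect size or precision for Aim 3, so there is no figure of the plan's own to reproduce.

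**Inputs from the documents.** Sample Size Calculation: "We will randomize up to 70 patients with ESLD for this project", allocated 1:1, so at most 35 per arm. Critical values are 0.05 and 0.20 (Analysis Plan); two-sided testing is assumed because sidedness is not stated.

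**Assumed inputs (not in the documents).** Baseline rate of 'No', the share who keep it, the share who convert to it, no dropout, and each item reduced to 'No, do not attempt' versus other.

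**1. What the McNemar pair can show when there is no video effect.** Let s be the chance that one arm's exact McNemar test is significant, found by enumerating patients who gain, lose or stay at 'No' with n = 35. If both arms have the same true switching, then P(video significant, narrative not) = s(1 − s). With 3% moving away from 'No', at 0.05:

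| Patients moving to 'No', both arms | Video arm only |
|---|---|
| 5% | 0.3% |
| 10% | 5.5% |
| 20% | 25% (s = 0.44; 0.44 × 0.56) |
| 30% | 16% |
| 40% | 4% |

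The function s(1 − s) cannot exceed 25%. Exactly one arm being significant, in either direction, has probability 2s(1 − s): 11% at a 10% shift and 49% at a 20% shift. Half of that is narrative-only. At 0.20 the 20% shift gives 40% for exactly one arm, hence 20% video-only.

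*Example.* In the video arm 9 patients move to 'No' and 1 away: p = 2 × (1 + 10)/1024 = 0.021. In the narrative arm 5 move to and 1 away: p = 2 × (1 + 6)/64 = 0.22. Starting from 10 and 14 'No' answers, both arms finish at 18 of 35 (10 + 9 − 1 and 14 + 5 − 1), and Fisher's p is 1.0.

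**2. What using the baseline answer gains.** Main scenario: baseline 'No' 30%, 95% keep it, conversion 20% (narrative) versus 50% (video).

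- Post-intervention 'No': narrative 0.30 × 0.95 + 0.70 × 0.20 = 0.425; video 0.30 × 0.95 + 0.70 × 0.50 = 0.635; difference 21 points.
- Crude SE: √[(0.425 × 0.575 + 0.635 × 0.365)/35] = 0.117; simulated, 11.6 points.
- Baseline-standardised SE: simulated, 9.7 points. The ratio (11.6/9.7)² = 1.43 is worth about 43% more patients.

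Power at 0.05, post-only Fisher against the exact test stratified by the two-category baseline answer (simulation; error about 1 point):

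| Baseline 'No' | Keep 'No' | Convert (narrative / video) | Fisher | Stratified exact |
|---|---|---|---|---|
| 30% | 95% | 20% / 50% | 31% | 50–51% |
| 50% | 95% | 20% / 50% | 19% | 32–33% |
| 30% | 70% | 20% / 50% | 32% | 42% |
| 30% | 60% narrative, 75% video | 30% / 50% | 24% | 31–32% |

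At 0.20 the main scenario gives 58% against 76%. With no video effect, the stratified test rejects in about 3% of trials at 0.05 and 15% at 0.20, so it keeps its level.

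**3. How far this depends on the baseline–post association.** The variance ratio of adjusted to unadjusted difference is roughly 1 − φ², where φ is the correlation between the two answers. Simulated ratios run from 0.47 (φ about 0.74) to 0.95 (φ about 0.26). At φ = 0.26 and an 18-point difference, power is 28% for Fisher, 36% for an unadjusted chi-square and 37% for a large-sample stratified test. Almost all of that gap is Fisher's conservatism (actual size 2.4% at nominal 0.05 when both arms are at 50%), not the unused baseline.

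**The case against.** The strongest reply is that the plan already has a proper test. Fisher's exact test on the post-intervention answers matches the between-arm wording of Hypotheses 3 and 4, and randomization after the baseline questionnaire keeps it unbiased. The critical values are introduced as "critical values to assess statistical significance between the two arms in this pilot study", which points to Fisher rather than McNemar. The McNemar tests can be read as describing the separately listed before-and-after outcome. All of this stands.

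A reader might infer that the plan means to claim Hypothesis 4 when the video arm is significant and the narrative arm is not. The documents do not support that: no sentence assigns a hypothesis to the McNemar results, and for EOL preference (Hypothesis 3) there is no McNemar test to misread. Nor is 49% the rate of a misleading video result; the relevant figure is at most 25% per item.

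It is also fair to say that these are secondary outcomes of a pilot whose primary outcome is feasibility and whose size was not set by power, and that the precision gain rests on an association the documents do not report. What the reply does not answer is that baseline answers already held for every patient go unused in comparing the arms, and that the role of the McNemar tests is left open.

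**Conclusion.** The point holds as one of efficiency and clarity, not of bias. Aim 3's between-arm test is valid but omits the baseline answers. Under the assumed rates at 35 per arm, stratifying by them raises power at 0.05 from about 19–32% to about 32–50%. The gain is large if answers are stable and small if the association is weak, and part of it reflects Fisher's conservatism. It would go too far to say that much precision is certainly lost. The calculations are for two-category answers; none was done for the four-category EOL item.

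The McNemar p-values cannot support a between-arm claim. With equal true shifts of 10–25% and 3% moving away, video-only significance arises in about 5–25% of trials per item at 0.05, and more rarely with very small or very large shifts. This is a misreading that the wording permits, not a rule that the plan states. The change is worth making because it is almost free.

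**What to change.** Replace both Aim 3 sentences. Changing only the McNemar sentence would leave two between-arm tests competing for the same hypotheses. Suggested content:

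- **Outcomes:** comfort care versus other; 'No, do not attempt CPR' versus other; 'No, do not attempt intubation' versus other. 'Unsure' and 'Not sure' count as other. This also settles how the three-option items are reduced to two categories, which the plan leaves unstated.
- **Deciding test:** for each outcome, an exact Mantel-Haenszel comparison of the arms, stratified by the same two-category baseline answer, with a baseline-standardised risk difference and 95% CI. This test alone decides Hypotheses 3 and 4. Two strata are used because three or four would be thin with at most 70 patients.
- **Supportive:** the unadjusted Fisher's exact test on the full post-intervention categories.
- **Descriptive:** within-arm before/after changes as counts, stated not to be evidence of a video effect.

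The cost is revised wording and slightly more analysis. All data are already collected, and no patients or visits are added. The downside is little gain if baseline answers turn out to predict post-intervention answers weakly.

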of the study: to better understand how much patients with ESLD know about ACP and EOL care preferences. The RA will also explain that the study requires completing a 15-minute baseline questionnaire asking participants about their CPR and intubation preferences, eliciting prior advance care planning discussions, and assessing their knowledge regarding CPR and intubation. The RA will undergo standardized training in all aspects of the research protocol, including the use of structured scripts to administer the questionnaires (**Appendix A**). For patients agreeing to participate in the study, the RA will obtain written informed consent from the participants and provide them with a copy of the signed consent form.

After obtaining informed consent, the RA will administer the Short Portal Mental Status Questionnaire (**Appendix B**) to participants to confirm final eligibility. Immediately following enrollment, the RA will administer a 15-minute baseline questionnaire (see “Study Measures” below) that will include the following: demographics, self-reported health status, baseline EOL care preferences, CPR and intubation preferences, and a questionnaire assessing patients’ knowledge of EOL care options.

Randomization

After enrollment and completion of the baseline questionnaires, participants will be randomized in 1:1 fashion without any stratification to either the control group (verbal narrative alone) or the intervention group (video decision support tool) using a random computer generated list, with assignments concealed in numbered envelopes.

The Intervention Arm

Our group, the VIDEO Consortium (Video Images of Disease for Ethical Outcomes), has developed several video decision support tools to assist patients with advance care planning.^{38,39,44} We have previously developed a five-minute advance care planning video for patients with advanced cancer⁴⁵, which has been adapted for this study.

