Aim 4: Code status documentation will be compared between the two groups using Fisher's exact tests.

Project Timeline	Table 1: Study Timeline and Study Procedures
Months 0-2	❖ Finalize protocol development and submit to Institutional Review Board for approval
Months 3-24	Data Collection ❖ Enroll up to 70 patients to participate in the prospective study ❖ Collect follow-up data on ACP documentation and prepare manuscript(s) for publication

REFERENCES

A Randomized Controlled Trial of an Advanced Care Planning Video Decision Support Tool for Patients with End-Stage Liver Disease

Version 9: February 6, 2020

8. Dying in America: improving quality and honoring individual preferences near the end of life. *Mil Med*. 2015;180(4):365-367.
10. Gillick MR. Advance care planning. *The New England journal of medicine*. 2004;350(1):7-8.

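### In Aim 4's yes/no code status comparison, Fisher's exact test is valid but conservative; Boschloo's exact test would recover some power at the same error levels (optional improvement)

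*Combined protocol and SAP*

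**What the plan says.** All references are to the combined protocol and SAP.

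- **Levels.** The opening of the Analysis Plan says "we will use conservative ($\alpha = 0.05$) and liberal ($\alpha = 0.20$) critical values to assess statistical significance". The reason it gives is that the study is a pilot.
- **Aim 4.** "Code status documentation will be compared between the two groups using" Fisher's exact test. Study Measures defines the outcome as yes or no, read from the record 3 months after enrolment.
- **Aim 3.** End-of-life care preferences, "CPR preferences, and intubation preferences will be compared between the two groups using" the same test. The Analysis Plan lists three end-of-life categories and Study Outcomes lists four. CPR and intubation each have three possible answers, and no rule collapses them to two.
- **Design.** The Randomization section says "participants will be randomized in 1:1 fashion without any stratification", from a computer-generated list. Blocking is not mentioned.
- **Size.** Sample Size Calculation says "We will randomize up to 70 patients with ESLD for this project" and rests that number on the project timeframe and on assessing preliminary efficacy. It gives no power, effect size or control rate for Aims 3 and 4. The tests are not stated to be one- or two-sided.

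**The concern.** Fisher's test conditions on both margins of the table. In this trial only the arm sizes are set by design; the total number of patients with a documented code status is random. With small arms the conditional distribution is coarse. The chance of a false positive can then sit well below the chosen critical value, and power falls with it.

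That sits awkwardly with a 0.20 level chosen to be liberal in a pilot. If the test spends only part of the allowance, some of the sensitivity that the level was meant to provide is lost. An exact test that does not condition on the random margin can recover part of it without enrolling anyone else.

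**Working it through.** **No stated figure to reproduce.** The values 0.05 and 0.20 are chosen thresholds, and the plan gives no power for this comparison. The check is therefore an exact calculation from the design.

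**Inputs.** Critical values 0.05 and 0.20 (Analysis Plan). Total of at most 70, 1:1 (Sample Size Calculation, Randomization). Binary outcome (Study Measures). Assumptions: two-sided tests; 35 per arm first, then imbalanced splits; documentation rates from 10% to 70%. The 28% used in some pairs is the advance-directive rate in Background and Significance. It is a different measure and serves only as an illustration.

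**Step 1: size of Fisher's test.** Let P(x, y) be the two-sided Fisher p-value when x of n1 and y of n2 patients have documentation. For a common rate θ,

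size(θ) = Σx Σy Bin(x; n1, θ) · Bin(y; n2, θ) · 1[P(x, y) ≤ α].

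This was summed over all tables (36 × 36 = 1,296 at 35/35) and maximised over a grid of 1,999 values of θ.

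**Step 2: Boschloo's test.** Its p-value is the maximum over θ of Pr[P(X, Y) ≤ observed P]. Because Fisher's test is valid, that maximum cannot exceed the observed P. Boschloo's p-value is therefore never larger than Fisher's, so it rejects whenever Fisher does, and its size stays at or below α.

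| Arms | Fisher max size, α 0.05 | Fisher, α 0.20 | Boschloo, α 0.05 | Boschloo, α 0.20 |
|---|---|---|---|---|
| 35/35 | 2.9% | 13.2% | 4.8% | 19.2% |
| 34/35 | 3.9% | 16.6% | 4.9% | 19.6% |
| 34/36 | 3.8% | 16.0% | 4.9% | 19.8% |
| 33/37 | 3.9% | 16.1% | 4.7% | 20.0% |
| 32/38 | 3.7% | 15.7% | 4.8% | 19.7% |
| 31/39 | 3.8% | 16.5% | 4.9% | 20.0% |

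At 35/35 the liberal level leaves (20 − 13.2)/20 = 34% of its allowance unused. At 34/36 it leaves (20 − 16.0)/20 = 20%. One-sided at 35/35, Fisher's maxima are 3.6% and 14.1%.

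**Step 3: power at 35/35**, by the same sum with different rates in the two arms:

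| Assumed rates | α 0.05, Fisher to Boschloo | α 0.20, Fisher to Boschloo |
|---|---|---|
| 10% v 30% | 45.5 to 54.2 (+8.7) | 71.9 to 78.8 (+6.9) |
| 20% v 50% | 69.2 to 75.7 (+6.5) | 87.8 to 91.3 (+3.5) |
| 28% v 50% | 38.3 to 45.3 (+7.0) | 63.6 to 71.6 (+8.0) |
| 28% v 60% | 69.4 to 76.2 (+6.9) | 88.5 to 92.5 (+4.0) |
| 40% v 60% | 28.0 to 36.1 (+8.1) | 55.3 to 64.7 (+9.4) |

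Gains are taken before rounding. Over eleven rate pairs (these five and 20 v 40, 28 v 48, 28 v 53, 28 v 58, 40 v 70, 50 v 70) the gain is 6.5 to 8.8 points at 0.05 and 3.5 to 9.4 at 0.20.

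**Step 4: power under imbalance.** The same eleven pairs were run at the five unequal splits above, with each arm in turn as the larger. The gain is 0.4 to 7.7 points at 0.05 (median 4.8, mostly above 2) and 0.0 to 8.2 points at 0.20 (median 2.9).

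**Step 5: one table by hand.** Take 10/35 against 19/35, with 29 documented in total. The hypergeometric tails are Pr(X ≤ 10) = 0.0257 and Pr(X ≥ 19) = 0.0257, so Fisher's p = 0.051. Boschloo's p = 0.032.

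**Step 6: Aim 3 as planned.** For 2x3 and 2x4 tables at 35/35, the extension of Fisher's test to larger tables (Fisher-Freeman-Halton) was run on 20,000 simulated null trials per scenario. Its size was about 4.6 to 4.8% at 0.05 and 18.5 to 19.9% at 0.20, close to nominal.

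**The case against.** There are four serious objections.

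1. **Fisher's test is not wrong.** It keeps the error at or below both thresholds, and the plan promises no attained rate. A reader might infer that the plan misstates its false-positive rates. It does not: it names critical values for p-values. This objection stands, and the point is therefore about efficiency only.

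2. **Aim 3 is mostly out of reach.** A reader might infer that the preference comparisons lose the same power. As written they are tables with three or four response categories, where Fisher's size is near nominal and a 2x2 test cannot be substituted. This also stands. Hypotheses 3 and 4 (prefer comfort care; forgo CPR and intubation) suggest binary contrasts, but the Analysis Plan does not specify them.

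3. **The 2.9% and 13.2% belong to exact balance.** The total is a ceiling and blocking is not stated. Under simple randomisation of 70, exactly 35/35 has probability C(70, 35)/2^70 = 9.5%. A difference of one patient already lifts the maxima to 3.9% and 16.6%. This stands as a limit on size. Fisher stays below nominal in every split tried, and Boschloo's power is never lower. Smaller equal arms do not remove the conservatism: Fisher's maxima are 3.6% and 12.7% at 33/33, and 2.7% and 15.5% at 30/30.

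4. **Little depends on it.** Feasibility is the primary endpoint, code status is not among the listed secondary outcomes, and the stated use of the data is to estimate an effect size for later trials. Estimates do not change with the choice of p-value. This is fair, and it is why the change is optional.

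**Conclusion.** The point holds for Aim 4 as an inexpensive improvement. Fisher's test leaves part of both allowances unused, and Boschloo's test recovers some of the lost power without exceeding either level. The benefit is largest at exactly 35/35. It can be close to nothing for some unequal splits and rates, and at 35/35 it falls to about 2 points or less once Fisher's power passes about 95%.

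The size of the gain rests on two-sided testing, on the arm sizes reached, and on assumed documentation rates. That Boschloo's test is never less powerful depends on none of these rates, provided that its ordering statistic is the two-sided Fisher p-value. The documents do not support treating the gap as a fixed property of the plan or as a fault in its error control.

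**What to change.** - **Aim 4.** Replace Fisher's exact test with two-sided Boschloo's unconditional exact test, and name the two-sided Fisher p-value as the ordering statistic. Naming it matters: a two-sided version built another way is not covered by the argument that it rejects whenever Fisher does. Report the risk difference with a 95% CI, and show the Fisher p-value alongside for comparison with earlier studies. The interval also serves the stated purpose of informing the effect size for later trials.
- **Aim 3.** Use Boschloo's test only for a preference that the plan defines as binary, for example comfort care against all other answers, or forgoing CPR against all other answers. Leave the planned Fisher tests on three or four categories as they are.

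The cost is one line of SAP text and a short calculation, with no added patients. The drawback is that clinical readers know the test less well, which showing the Fisher p-value beside it partly offsets.
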